### 6.4. Worst-case

A worst-case analysis visit will be created for parameters for which abnormalities and/or toxicity grades (e.g., labs, vital signs, ECGs) are defined to summarize values considered as the worst-case. For abnormalities worst-case is derived per parameter and in case both the lowest and the highest values are considered abnormal, a participant can have two worst-case analysis visits for a same parameter. For toxicity grades the worst-case is the value associated to the highest toxicity grade and is derived per parameter and toxicity direction (hypo / hyper).

All non-missing post-baseline values, including unscheduled assessments will be considered when deriving the worstcase analysis visit.

## 6.5. Treatment-emergent Abnormality/Toxicity

A treatment-emergent abnormality/toxicity (for laboratory assessments, vital signs, or ECGs) is defined as any

Document: BIOSdata\argenx\Efgartigimod\HAB40220\Biostatistics\Documentation\SAP

1.0 Author: Version Number:

> Version Date: 03 June 2024

Template No.: CS\_TP\_BS016 Revision 7 Reference: CS\_WI\_BS005

<sup>b Post baseline visit Day 1.

Page 23 of 54

postbaseline abnormality/toxicity that was not present at baseline (eg, hemoglobin normal at baseline and grade 1 postbaseline; glucose low at baseline and high postbaseline; QTcF [450; 480] ms at baseline and >500 ms postbaseline).

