Version Date: 03 June 2024

Template No.: CS\_TP\_BS016 Revision 7 Reference: CS\_WI\_BS005

Page 25 of 54

For frequency tabulations and cross-tabulations, the denominator will be the number of participants per treatment arm. For tables where results are shown by analysis visit, the denominator will be the number of participants per treatment arm and analysis visit. Missing values will not be included in the denominator count when computing percentages. For cross-tabulation of post-baseline results versus baseline results, a "missing" category will be shown for baseline results, if applicable. Percentages will be presented with 1 decimal place.

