- Laboratory toxicity grades to be presented as cross-tabulations of the toxicity at each postbaseline analysis visit and at the worst-case analysis visit versus the baseline toxicity for SAF at the IA and FPA.
- Laboratory abnormalities as cross-tabulations of the abnormality at each postbaseline analysis visit and at the worst-case analysis visit versus the baseline abnormality for SAF at the IA and FPA.
- The number of participants with treatment-emergent abnormalities will also be shown. The denominator for the percentage is the total number of participants per treatment arm and per analysis visit in the SAF.
- Listing of participants with any post-baseline abnormality or toxicity grade  $\geq 1$ .

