### 14.3. ECG Evaluations

Results from the central ECG (Electrocardiogram) Reading Centre will be included in the reporting of this study. Single 12-lead ECG(s) will be obtained using an ECG machine. The following ECG parameters will be reported for this study:

- HR (bpm)
- PR Interval (msec)
- QRS Interval (msec)
- RR Interval (msec)
- QT Interval (msec)
- QTcF Interval (msec)
- QTcB Interval (msec)

All datapoints obtained after informed consent up to database cutoff will be considered.

The following summaries will be provided for ECG data:

ECG parameters will be summarized using descriptive statistics at each analysis visit for the SAF for FPA only.

Abnormalities of the actual values will be presented as cross-tabulations of the abnormality at each postbaseline analysis visit and at the worst-case analysis visit versus the baseline abnormality. Numbers and cumulative numbers (QTc only) of participants with treatment-emergent abnormalities will also be shown. The denominator for the percentage is the total number of participants per treatment arm and per analysis visit in the SAF for FPA only.

Abnormalities of the QTc changes will be presented as tabulations of the change abnormality at each postbaseline analysis visit and at the worst-case analysis visit. Cumulative numbers of participants with change abnormalities will also be shown. The denominator for the percentage is the total number of participants per treatment arm and per analysis visit in the SAF. Produced for the FPA only.

All ECG data will be listed, but only for participants with any postbaseline abnormality.

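### The treatment-emergent rule in SAP 6.5 has no worsening condition, so a fall between abnormal QTc categories counts as a new abnormality

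*SAP*

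**What the plan says.** SAP 6.5 covers laboratory assessments, vital signs and ECGs. It defines treatment-emergent as any "postbaseline abnormality/toxicity that was not present at baseline" and gives three examples: haemoglobin normal at baseline and grade 1 later, glucose low at baseline and high later, and "QTcF [450; 480] ms at baseline and >500 ms postbaseline".

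SAP 14.3.1 sorts actual QT, QTcB and QTcF values into four ordered categories: normal (up to 450 ms), 450 to 480, 480 to 500, and above 500. SAP 14.3 then plans: "Numbers and cumulative numbers (QTc only) of participants with treatment-emergent abnormalities will also be shown". These ECG outputs are for the final analysis only.

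For laboratory data, SAP 14.2 plans: "The number of participants with treatment-emergent abnormalities will also be shown". SAP 14.2.1 defines the abnormality categories there as Low, Normal and High. Grades are handled separately: "Laboratory toxicity grades to be presented as cross-tabulations of the toxicity at each postbaseline analysis visit", set against the baseline grade.

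**The concern.** A treatment-emergent count is normally read as the number of participants who got worse on treatment. SAP 6.5 asks only whether the postbaseline category is absent at baseline. For a two-state variable the two ideas coincide. For ordered abnormal categories they do not, because a milder category is also absent at baseline when the participant started in a more severe one.

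ECG results are named in the primary safety endpoint (SAP 2 and 14). The planned QTc count could therefore include participants whose QTc shortened, with nothing in the count to separate them from those whose QTc lengthened.

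**Working it through.** The plan states no treatment-emergent rate, so there is no figure to reproduce. The check is to list the category changes that each reading of SAP 6.5 would count.

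**Which reading the SAP supports.** If 'not present' meant normal at baseline, the QTcF example would not qualify, because that participant starts at 450 to 480 ms. Nor would the glucose example, which starts low. The SAP therefore compares categories.

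**Counting rule as written.** A change from baseline category b to postbaseline category p counts if p is abnormal and p differs from b. With k ordered categories, one of them normal, the number of countable changes is k(k − 1) − (k − 1) = (k − 1)². Of these, (k − 1)(k − 2)/2 are improvements.

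- QTc, k = 4: 3² = 9 countable changes, of which 3 × 2/2 = 3 are improvements (above 500 to 480–500, above 500 to 450–480, and 480–500 to 450–480). The other 6 are worsenings.
- CTCAE grades 0 to 4, k = 5: 4² = 16 countable changes, of which 4 × 3/2 = 6 are improvements (2 to 1, 3 to 1, 3 to 2, 4 to 1, 4 to 2, 4 to 3). The other 10 are worsenings. This is for a parameter with all four grades; some rows of SAP Appendix 2 have fewer.
- Low/Normal/High: the countable changes are normal to low, normal to high, low to high and high to low. None is an improvement. The extra combined low-and-high category at the worst-case visit always contains an abnormality that a single baseline value did not have, so it adds none.

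**The alternative reading.** Counting only participants who were normal at baseline removes every improvement. It also loses 3 of the 6 QTc worsenings and 6 of the 10 grade worsenings, and it contradicts two of the SAP's own examples.

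**Size.** The only participant number available is the approximately 38 expected in SAP 3.2, used here as an assumed denominator. One improver adds 1/38 = 2.6%. The number of improvers is not given. Over an assumed range of 0 to 4, the false addition runs 0%, 2.6%, 5.3%, 7.9% and 10.5% (0/38 to 4/38). Actual denominators are per analysis visit and may be smaller.

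**With a worsening condition.** Countable changes fall from 9 to 6 for QTc and from 16 to 10 for grades, and stay at 4 for Low/Normal/High. All three SAP examples still count: two are worsenings and one is a change of direction.

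**The case against.** The strongest reply is that this is a drafting gap and not an intended rule. Every example in SAP 6.5 is a worsening or a change of direction, and a careful programmer would probably apply it that way. That stands as to intent, but the sentence to be programmed still lacks the condition.

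A second reply concerns the cumulative QTc counts. The SAP does not define cumulative. If it means exceeding successive thresholds, a participant above 500 ms at baseline already exceeds 450 and a fall is not new. On that reading the exposure is mainly in the non-cumulative counts, which SAP 14.3 also plans.

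Third, SAP 14.2 and 14.3 plan cross-tabulations against baseline, per visit and at worst case. A reader could rebuild a correct count from them. This limits the harm, but the figure labelled treatment-emergent would still be wrong.

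Two stronger readings are tempting, and the documents do not support them.

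- A reader might infer that laboratory treatment-emergent counts in general are inflated by improvements. The count that SAP 14.2 names is for Low/Normal/High, where no improvement can enter, and grades are planned as cross-tabulations. Grades are exposed only if treatment-emergent toxicity is tabulated, which the title of SAP 6.5 allows but SAP 14.2 does not list.
- A reader might infer that the percentage is diluted, because "The denominator for the percentage is the total number of participants per treatment arm and per analysis visit in the SAF", with no exclusion for baseline status. That denominator is a conventional choice. Under the category comparison, a participant already abnormal can still become emergent in another category, so removing all such participants would be wrong. Missing values are addressed in SAP 7.2: "Missing values will not be included in the denominator count when computing percentages". The baseline abnormality rate needed to size any dilution is not given.

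**Conclusion.** The point holds for ordered abnormal categories. As written, SAP 6.5 counts an improvement from a more severe to a milder QTc category as treatment-emergent in the SAP 14.3 counts. It would do the same for CTCAE grades if treatment-emergent toxicity is tabulated. Low/Normal/High counts for laboratory, vital-sign and other ECG parameters are unaffected, and no change to the denominator is called for.

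The total size cannot be fixed from the documents. Each improver adds one false event, about 2.6% if 38 participants contribute. This rests on reading the definition literally and by category, as its QTcF example requires. It does not show that the sponsor means to count improvements. The adverse event summaries do not use this rule. It is a small correction to a stated rule.

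**What to change.** In SAP 6.5, define treatment-emergent as a postbaseline category or grade that is worse than baseline in the same direction, or an abnormality in the opposite direction to baseline. Apply it to the QT, QTcB and QTcF categories of SAP 14.3.1 and, if treatment-emergent toxicity is tabulated, to CTCAE grades by direction (hypo or hyper, as SAP 6.4 already separates them).

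The cost is one sentence and the matching program condition. No new data or outputs are needed, and the three existing examples can stay as they are.

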; AE=adverse event; BL=baseline; COMPASS=composite autonomic symptom scale; Conmed=concomitant medications; CRP=C-reactive protein; ESR=erythrocyte sedimentation rate; IMP=investigational medicinal product; MaPS=Malmö POTS Symptom Score; PD=pharmacodynamics; PGI-C=Patient Global Impression – Change; PGI-S=Patient Global Impression – Severity; PK=pharmacokinetics; POTS=postural orthostatic tachycardia syndrome; PROMIS=Patient-Reported Outcomes Measurement Information System; QW = once weekly; Q2W = every 2 weeks; TSH=thyroid stimulating hormone; W=week; WOCBP=women of childbearing potential.

<sup>a With the exception of informed consent, eligibility check, and IMP infusion, assessments at BL are conducted as part of the ARGX-113-2104 study.

- b Questionnaires will be administered in the following order: MaPS, PGI-S past week recall, PROMIS Fatigue, PROMIS Cognitive Function, COMPASS 31, PGI-S 2-week recall, PGI-C.
- c Procedure performed as part of the ARGX-113-2104 study week 24 assessments
- d These assessments may be performed over 1 to 2 days at each time point, as long as all testing is completed prior to dosing scheduled for that time point.
- e The physical examination will comprise a full assessment of systems at baseline and a brief assessment at all other time points.
- f The 10 mg/kg efgartigimod dose is based on body weight, and the maximum total dose per efgartigimod infusion is 1200 mg for participants who weigh ≥120 kg. The dose level will be recalculated if a participant's weight has changed (increased or decreased) by more than 10% from baseline.
- g Vital signs will be measured before collecting any blood sample or administering IMP infusions.
- h A urine pregnancy test will be conducted for WOCBP at baseline and during the study, including during the follow-up period. On visits where both pregnancy testing and IMP administration will be performed, all pregnancy testing must be performed predose. Dosing should not begin until a negative pregnancy test result has been confirmed.
- i Blood samples to be collected predose (except for week 48, where no IMP is administered and the sample can be taken at any time during the visit).

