### 2. INTRODUCTION

In Study ARGX-113-2104, the efficacy and safety of efgartigimod IV in adult patients with PC-POTS is evaluated using a randomized, double-blinded, placebo-controlled study design. Participants are randomized to receive efgartigimod IV 10 mg/kg or matching placebo in a 2:1 ratio. The IMP (efgartigimod or matching placebo) is administered during the treatment period in an approximately 1-hour IV infusion QW by site staff or a home nurse. The final dose is administered at week 23. At week 24, eligible participants from ARGX-113-2104 may roll over into the present single-arm OLE study: ARGX-113-2105.

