### 6.2. Baseline

Unless otherwise specified, baseline is defined as the last available non-missing measurement per parameter from the parent study 2104. Refer to appendix 1 baseline for details.

Assessments performed on the same day as the first IMP administration but without time information collected or with time information exactly equal to the time of first IMP administration and which are planned predose will be considered as predose.

Adverse Events (AEs) and medications commencing on the reference start date will be considered post-baseline unless otherwise indicated based on available start date/time combination or collected electronic case report form (eCRF) information that identifies the individual event/medication as starting prior to first IMP administration.

The baseline visit for Study 2105 will be conducted after the participant has finished in 2104 and completed week 24

Document: BIOSdata\argenx\Efgartigimod\HAB40220\Biostatistics\Documentation\SAP

1.0 Author: Version Number:

> Version Date: 03 June 2024

Template No.: CS\_TP\_BS016 Revision 7 Reference: CS\_WI\_BS005

analysis. All baseline assessments will be performed before first administration of efgartigimod IV in ARGX-113-2105, if applicable. Assessments do not need to be repeated if they are performed as part of 2104.

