## 15.2. Pharmacodynamic Analysis

Pharmacodynamic (PD) effect of efgartigimod will be assessed via Total IgG. PD analyses will be performed in the SAF for IA and FPA.

Two analyses will be presented, one using the baseline of the parent study (2104); and the other using the baseline of the present OLE study (2104 week 24 visit/ARGX-113-2105 baseline/day 1).

Total IgG will be summarized using descriptive statistics at each analysis visit. Absolute values, changes from baseline, and percent reduction from baseline will be presented. In addition to the planned time points, the following time points will also be shown:

- Maximum drop from baseline
- Minimum post baseline value

All PD data will be listed.

Document: BIOSdata\argenx\Efgartigimod\HAB40220\Biostatistics\Documentation\SAP

Author: Version Number: 1.0

Version Date: 03 June 2024

Template No.: CS\_TP\_BS016 Revision 7 Reference: CS\_WI\_BS005

Effective Date: 01Nev2021

Page 41 of 54

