#### Baseline for these data will use 2105 baseline data

Description	Source
Vital Sign	EDC data: VS
Adverse Events	EDC data: AE
Prior and Concomitant Medications	EDC data: CM
Medical History	EDC data: MH
Date of Visit	EDC data: VIS
Study Continuation	EDC data: STDYCON
Pandemic Visit Impact	EDC data: VIS_PAND
IRT	Non-EDC data: IRT

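### Laboratory, ECG and vital-sign shifts have no pre-efgartigimod reference: the only baseline is OLE entry, which is on drug for about two-thirds of participants

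*SAP*

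**What the plan says.** **Definition.** SAP 6.5 covers laboratory tests, vital signs and ECG, and treats as emergent any "postbaseline abnormality/toxicity that was not present at baseline".

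**Baseline.** SAP 6.2: "baseline is defined as the last available non-missing measurement per parameter from the parent study 2104". The footnote to the protocol's Schedule of Activities (1.3) on the baseline laboratory, vital-sign and ECG assessments reads "Procedure performed as part of the ARGX-113-2104 study week 24 assessments". SAP Appendix 1 lists vital signs under a different heading, "Baseline for these data will use 2105 baseline data", but that is still OLE entry.

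**Parent study.** Protocol 2: "Participants are randomized to receive efgartigimod IV 10 mg/kg or matching placebo in a 2:1 ratio". Dosing there is weekly, and "The final dose is administered at week 23".

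**Outputs that use this baseline.**
- Laboratory (SAP 14.2): change from baseline at each visit; "Laboratory toxicity grades to be presented as cross-tabulations of the toxicity at each postbaseline analysis visit" and at the worst case, against baseline; the same for abnormalities; and a count of participants with treatment-emergent abnormalities.
- ECG (SAP 14.3): cross-tabulations against baseline, treatment-emergent counts and QTc-change categories.
- Vital signs (SAP 14.4): cross-tabulations against baseline. No treatment-emergent count is named.

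**Where a second baseline is planned.** For total IgG, SAP 15.2 says "Two analyses will be presented, one using the baseline of the parent study (2104); and the other using the baseline" of the OLE. Protocol 9.3.3.1 adds change from the parent-study baseline for COMPASS 31 and MaPS. Nothing similar is planned for laboratory tests, ECG or vital signs, which belong to the primary endpoint.

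**The concern.** The primary objective is the long-term safety of efgartigimod. Participants who had efgartigimod in 2104 have the longest exposure, yet their reference value is taken about one week after an active dose. An abnormality that developed on drug in 2104 and persists unchanged through the OLE counts as present at baseline, so it carries no treatment-emergent flag. A QTc rise already reached by 2104 week 24 gives a change near zero and falls in the normal change category.

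The reader can still see that such a participant is abnormal, but cannot tell whether the abnormality arose on efgartigimod or predates it. An overall summary also mixes two quantities: change since before drug (former placebo) and change since week 24 on drug (former efgartigimod).

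The sponsor already treats some analytes as able to reveal treatment. Albumin and total protein are blinded to protect the 2104 blind, and albumin is toxicity-graded in SAP Appendix 2.

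**Working it through.** **Inputs from the documents.** About 38 roll-overs at about 90% of the parent study (protocol 9.5, SAP 3.2); 2:1 allocation (protocol 2). The documents state no count or rate of treatment-emergent abnormalities, so there is no planned figure to reproduce.

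**Step 1: share on drug at OLE entry.**
- Implied parent size: 38 / 0.90 = 42.2. Check: 0.90 × 42 = 37.8, about 38. The parent sample size itself is not in the documents.
- With equal roll-over, 38 × 2/3 = 25.3 former efgartigimod and 12.7 former placebo; take 25 and 13.
- With 42 split 28:14 and all 4 non-rollovers from the efgartigimod arm, the share is 24/38 = 63%. With all 4 from placebo, it is 28/38 = 74%.

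**Step 2: what each planned output shows for a participant who became abnormal on efgartigimod in 2104.**

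| Course in the OLE | Treatment-emergent (SAP 6.5) | Shift tables and listings |
|---|---|---|
| Same category persists | No | Shown as abnormal to abnormal |
| Category worsens or direction changes | Yes, by the SAP's own QTcF and glucose examples | Shown as a shift |

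The first row is the gap. The abnormal-to-abnormal cell holds both abnormalities that arose on efgartigimod and abnormalities that predate it.

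**Step 3: possible size, per parameter.** Let q be the share of the 25 former efgartigimod participants who enter with an abnormality that arose on drug and persists unchanged. Let r be the share of participants not already abnormal who develop a new one in the OLE. Neither is in the documents. Assume r = 10% in both parent groups.

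- Count against OLE entry = 25(1 − q)r + 13r
- Count against a pre-efgartigimod value = 25[q + (1 − q)r] + 13r
- Difference = 25q

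For q = 5%:
- OLE entry: 25 × 0.95 × 0.10 + 1.3 = 3.675, or 9.7% of 38
- Pre-efgartigimod: 25 × 0.145 + 1.3 = 4.925, or 13.0%

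For q = 10%:
- OLE entry: 25 × 0.90 × 0.10 + 1.3 = 3.55, or 9.3%
- Pre-efgartigimod: 25 × 0.19 + 1.3 = 6.05, or 15.9%

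The differences are 1.25 and 2.5 participants. The chance that at least one of the 25 is affected in a given parameter is 1 − 0.95^25 = 72% at q = 5%, and 1 − 0.90^25 = 93% at q = 10%.

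**The case against.** The strongest reply is that the chosen baseline fits the question asked. Protocol 4.2 describes the primary outcome as safety over about a year after 2104 ends, protocol 9.3.1.1 ties the outcomes to efgartigimod as given in the OLE, and SAP 14.1 starts treatment-emergent adverse events at the first 2105 dose. Abnormalities arising in 2104 belong to that study, whose analysis plan is not available here. The OLE is descriptive. This stands, and it is why the point is an improvement and not an error. It does not argue against a supplementary reference, since the plan already adds one for secondary endpoints. A report confined to 2104 also could not show whether an abnormality persists to OLE week 48.

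A second reply is that protocol 9.3.1 already requires summaries by parent treatment. That is correct, and it limits the pooling problem, although SAP 14.2 to 14.4 do not name the split and SAP Appendix 1 shows a single treatment group. Splitting by arm does not change the on-drug reference within the former efgartigimod group.

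A reader might infer that persistent abnormalities are never counted at all. The documents do not support that. The cross-tabulations tally them at each visit and at the worst case, actual laboratory values are summarised, the listings take in participants with any post-baseline abnormality, and worsening still counts as emergent.

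A reader might also infer a threefold understatement, by supposing that every abnormality starts within 24 weeks of first exposure, persists, and never starts later. The pooled OLE rate is then 13p/38 against p. That ratio is 38/13 = 2.9 for every p, so it is fixed by the assumption and says nothing about this trial.

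**Conclusion.** The point holds as a cheap improvement. For laboratory tests and ECG (treatment-emergent flags, shift tables, laboratory change from baseline and QTc-change categories) and for vital signs (shift tables), the only reference is OLE entry. That value is on drug for about 25 of 38 participants, or 63% to 74% if all non-rollovers came from one arm. What is missing is attribution: same-category abnormalities that arose on efgartigimod and persist cannot be separated from those that predate it.

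The size cannot be taken from the documents. Under the assumed rates above, the proportion per parameter rises from 9.7% to 13.0% or from 9.3% to 15.9%. These rest on 25 and 13 participants, the same new-onset rate in both parent groups, and no participant who was abnormal before efgartigimod, normal at OLE entry and abnormal again later. Such a participant would count only against the OLE-entry value. The two proportions answer different questions (new since OLE entry, and new since first efgartigimod), so the gap between them is not a bias in the planned table.

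**What to change.** Keep all OLE-baseline tables. Add to SAP 6.2 a pre-efgartigimod baseline: the last value before the first 2104 dose for former efgartigimod participants, and the OLE-entry pre-dose value for former placebo participants.

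In SAP 14.2 to 14.4, add against this baseline:
- worst-case shift tables for laboratory tests, ECG and vital signs;
- change from baseline where it is already planned (laboratory values and QTc categories);
- treatment-emergent counts for laboratory tests and ECG.

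Show these by parent arm, as protocol 9.3.1 requires, and overall. State that only OLE values count as post-baseline in these tables, because including 2104 on-treatment values would change the worst case.

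The cost is one more set of existing outputs and an extra import. For laboratory tests and ECG, SAP Appendix 1 brings over only the latest non-missing 2104 value, so the 2104 pre-dose laboratory, ECG and vital-sign values would have to be added. That they were collected is an assumption. If so, no new data collection, visit or change in trial conduct is needed.
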